13.3 Blinded Review Meeting

Once all subjects have completed Visit 6 and after discrepancy management and critical QC of the data are complete and before database lock for the double-blind phase, a blinded review of the study data will be performed to identify minor and major protocol deviations. In particular, in this meeting, subjects (and/or specific data) to be excluded from the per protocol (PP) set will be identified.

Once all subjects have completed the open-label extension phase and after discrepancy management and critical QC of the data are complete and before database lock for the open-label extension phase, a review of the study data will be performed to identify minor and major protocol deviations.

14. STATISTICAL ANALYSES

Further details of the proposed statistical analysis will be documented in the statistical analysis plan (SAP), which will be written following completion of the protocol and finalised prior to the breaking of the blind.

In general, safety and efficacy variables will be presented by means of descriptive statistics and figures, as appropriate, by treatment (active at each dose level and placebo) and by time point and gender, if applicable. Continuous variables will be summarised using the number of non-missing observations, mean, standard deviation (SD), median, first and third quartiles, minimum and maximum. Categorical variables will be presented using number of subjects and percentages. For ordered categorical variables, cumulative percentages may also be presented. Raw data will be listed.

Baseline values will be the last assessments prior to randomisation at Visit 2 unless stated otherwise.

A Bonferroni correction will be used to take into account that there are three active versus placebo comparisons; i.e. all p-values resulting from comparing the three different MED2005 doses (0.6 mg GTN, 1.2 mg GTN, 1.8 mg GTN) versus placebo will be multiplied by three and statistical significance will then be declared if $p < 0.05$. Corresponding Bonferroni corrected 95% confidence intervals will be produced.

The objective for the double-blind phase is for all co-primary endpoints to show superiority of MED2005 to placebo in order to conclude a significant result of the study. For this objective, no adjustment for multiplicity of the error probability for the individual co-primary endpoints is required. However, the three co-primary endpoints will still be considered in a hierarchy of their importance, with the testing order being IIEF-EF domain, SEP Question 3 and SEP Question 2.

The objective of the open-label extension phase is to evaluate the safety of long-term (up to 12 months) use of MED2005. In addition, the long-term efficacy of MED2005 will be evaluated. Both safety and efficacy will be evaluated in the subset of subjects who completed the double-blind phase and took part in the open-label extension phase. Descriptive statistics will be based on observed data. In case of any randomisation/treatment errors, any summaries split by treatment group will be produced according to treatment received.

Once all subjects have completed the double-blind phase (Visit 6), the database will be locked, treatment groups unblinded and the analysis of the double-blind phase will be performed using all data from the screening and double-blind treatment phases. A second analysis will be performed once all applicable subjects have completed the open-label extension phase.

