7.2 Secondary Objectives

- To evaluate the efficacy of MED2005 in male subjects using the Self-Esteem And Relationship (SEAR) questionnaire for men and women, the Global Assessment Questionnaire (GAQ), the additional domains of the IIEF, the Patient Global Impression of Severity (PGI-S), the Patient Global Impression of Change (PGI-C) as well as subjective measures of the time of onset and duration of action (erection) and erection hardness and questions on usage and application of MED2005
- To evaluate the long-term (up to 12 months) efficacy of MED2005
- To evaluate the safety of MED2005 using AEs and standard physico-chemical assessments

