8.2.3 Rationale for Study Drug Dose and Schedule

The justification for choice of doses to be tested in this study was based on PK and clinical data generated in earlier developmental studies with MED2005, and the clinical use of a 2.5 mg gel of GTN in a related FMD product.

FMD has previously tested the following doses of MED2005:

FMD study	Dose	Phase	Number of Volunteers/Patients
FM33	MED2003 0.075 mg, 0.1 mg, 0.25 mg, 0.5 mg MED2004 0.75 mg MED2005 1.2 mg	I	16 healthy volunteers
FM35	MED2003 0.01 mg, 0.075 mg, 0.25 mg MED2005 0.6 mg	I	15 healthy volunteers
FM53	MED2005 0.6 mg	IIa	232 patients
FM58	MED2005 0.6 mg, 1.2 mg, 1.8 mg, 2.4 mg	I	30 healthy volunteers

In the FM58 PK study, MED2005 0.6 mg, 1.2 mg, and 1.8 mg demonstrated similar or lower PK values than the sublingual tablet comparator (Nitrostat 1.8mg GTN); however, in some of the PK parameters the MED2005 2.4 mg was slightly higher compared to Nitrostat. There were no safety concerns for any of the studied doses of MED2005.

FMD currently market a condom based product with an ancillary medicinal substance. The class III medical device incorporates a topical gel which contains 2.5 mg GTN in a non-aqueous base and is used to help maintain an erection. Users are exposed to the topical application of 2.5 mg of GTN under the occlusion of the device. The extended clinical use of a 2.5 mg GTN gel in a class III has a validated satisfactory safety record.

Therefore MED2005 0.6 mg, 1.2 mg, and 1.8 mg were selected for the double-blind phase of this study. For the open-label extension phase, all subjects will be provided with MED2005 1.8 mg as this dose is expected to have the greatest efficacy and provide the most significant information on safety and efficacy.

During the double-blind phase subjects are asked to make at least four intercourse attempts using the IMP in each of the three 4-weekly period during treatment in order to get a reasonable assessment of the efficacy and safety of MED2005 versus placebo.

The open-label extension phase is designed to assess long-term safety of MED2005 as it might be used once it is on the market. Therefore, subjects will be asked to use the IMP as and when they wish to and medication use will be assessed as part of the open-label analyses.

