Other than for male/female sterilisation, if any of these above listed methods are being used then their effectiveness must be determined by the PI or their delegate, taking into consideration the compliance and tolerance of the female partner with this method of contraception.

Subjects who are or wish to become pregnant will not be included in the study.

7. Subject and his female partner are capable of understanding and complying with the requirements of the protocol and must have signed the ICF prior to participation in any study-related procedures
8. Low IIEF-EF scores (≤ 25) during the screening period

To continue in the open-label extension phase of the study, subjects must meet the following inclusion criteria at the follow-up visit of the double-blind phase (Visit 6):

1. Subject and his female partner complete the double-blind phase
2. Subject and his female partner were compliant to study procedures during the double-blind phase
3. Documented written informed consent from both subject and his female partner
4. If the male subject's female partner is of childbearing potential from the time of first sexual intercourse attempt during the screening period until the last administration of study treatment, then the couple must have been using a medically acceptable form of contraception for at least 3 months prior to entering the study, and agree to continue such use for at least 1 month after the last study drug administration

Acceptable methods of contraception are listed below; it should be noted that condoms, femidoms, diaphragms, caps or hormone rings are not permitted as a form of contraception in this study:

- Surgical sterilisation of the male partner (vasectomy with documentation of azoospermia if possible)
- The female partner has undergone documented tubal ligation (female sterilisation)
- The female partner uses combined hormone injectables
- The female partner uses medically prescribed hormonal implants
- The female partner has undergone documented placement of an intrauterine device (IUD) or intrauterine system (IUS)
- The female partner uses combined oral contraceptives
- The female partner uses progesterone only contraceptives
- The female partner uses combined hormonal patches

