14.1 Analysis Sets

The following analysis sets will be used for the statistical analysis of the double-blind phase:

- The **randomised set** will consist of all subjects who were randomised to a treatment
- The **safety set** will consist of all subjects in the randomised set who made use of the medication at least once. In the case of randomisation/treatment errors, subjects will be analysed according to treatment received

- The **full analysis set** (FAS) will consist of all subjects in the randomised set who made use of the medication at least once. In the case of randomisation/treatment errors, subjects will be analysed according to randomised treatment
Primary and secondary analyses will be performed on the FAS.
- The **per protocol set** (PP) will consist of all subjects in the FAS who completed the 12-week treatment period without major protocol violations and who have valid IIEF, SEP Question 2 and SEP Question 3 assessments at Week 12 (Visit 5)

Analysis sets will be identified prior to the unblinding of the study data. The efficacy analysis will be performed as randomised; i.e. a subject will be assigned to the treatment he was initially allocated, irrespective of what treatment was actually applied, and whether or not treatment was discontinued while questionnaire data was collected (see [Section 9.6](#) Withdrawal of Subjects).

In order to assess the consistency of results, sub-group analyses will also be performed according to three subject baseline ED severity groups:

- Mild (IIEF-EF domain score of 17–25)
- Moderate (IIEF-EF domain of 11–16)
- Severe (IIEF-EF domain of ≤ 10)

The following analysis set will be used for the statistical analysis of the open-label extension phase:

- The **open-label analysis set** (OLAS) will consist of all subjects who made use of medication at least once during the open-label extension.

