14.5.2 Handling of Missing Values

Full details on the handling of missing values in analyses of all analysis sets, including rules applied to incomplete questionnaires and planned additional analyses, will be defined in the SAP. Only the main principles are given for the analyses on the FAS here.

Summary statistics will present the number of missing values and then will be based on non-missing values.

Any missing values in efficacy questionnaire data that occur during the treatment period and are then followed by observed data shall be treated as missing at random and imputed using a corresponding multiple imputation approach.

All subjects who are withdrawn from the study will be asked to continue with the IIEF and SEP questionnaires if possible. These data will be used as part of the analysis for estimating the treatment effect over 12 weeks, according to the randomised treatment policy.

There can be remaining missing values for the primary endpoints for subjects who leave the study and provide no further questionnaire data. For these subjects, missing values will be handled using a control-based multiple imputation approach. The imputation model for the missing observations in both the MED2005 and placebo (control) groups will be constructed from the control group only (missing not at random [MNAR]). This assumes that efficacy results post withdrawal, for subjects who withdraw, would have mirrored those seen in the placebo group and thus lose any potential MED2005 treatment benefit.

Additional estimands/tests of treatment effect, beyond the primary treatment policy estimand, may be addressed, including exploring other ways of handling missing values, such as fitting repeated measures mixed models.

Summary statistics will present the number of observed values and will then be based on the non-missing values for the open-label extension phase.

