- The change in the other domains of the IIEF questionnaire, the other SEP questions (Questions 1, 4 and 5), the overall SEAR questionnaire score, the scores in the two subdomains of the SEAR questionnaire (sexual relationship satisfaction and confidence) and the PGI-S at time points 4, 8 and 12 weeks will be analysed using ANCOVA as described for the primary endpoint analysis for SEP Questions 2 and 3. The PGI-C will be analysed using an analysis of variance (ANOVA)
- Subjective measures of the time of onset and duration of action (erection) and erection hardness will be analysed using Wilcoxon ranks for each intercourse attempt, averaged across intercourse attempts within each 4-week period for each subject. The averaged Wilcoxon rank data will be analysed using ANCOVA as described for the primary endpoint analysis

- Usage and application question responses will be summarised by treatment group

All efficacy assessments provided by the female partners will be analysed using the same statistical models as for the male subjects.

Open-label extension phase:

Summary statistics for all efficacy measures will be given for actual values and changes from baseline (where applicable), where the baseline assessments are the ones prior to the double-blind phase. Individual components of composite scores (but not domains) will not be summarised unless otherwise stated. Individual components as well as domains will be presented in listings together with the scores used in the analysis.

Summaries of responders at each Visit will be given using the same responder definitions as per the analysis of double-blind phase.

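### Extension efficacy is summarised on whoever is still observed at each visit, so visit means can hold or rise through response-related attrition alone and cannot by themselves show lasting efficacy

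*Protocol*

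**What the plan says.** Section 7.2 lists as a secondary objective: "To evaluate the long-term (up to 12 months) efficacy of MED2005". Section 14 names long-term safety as the objective of the extension and adds efficacy to it. Both are to be "evaluated in the subset of subjects who completed the double-blind phase and took part in the open-label extension phase".

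The data rule appears twice. Section 14 says "Descriptive statistics will be based on observed data". Section 14.5.2 says "Summary statistics will present the number of observed values and will then be based on the non-missing values for the open-label extension phase".

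Entry is selective. Section 9.2 requires that both partners finished the double-blind phase and that "Subject and his female partner were compliant to study procedures during the double-blind phase". Section 8.1 leaves participation to the couple. All entrants receive the 1.8 mg gel without a control group, and section 8.2.3 says that "subjects will be asked to use the IMP as and when they wish to".

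The open-label analysis set (OLAS, section 14.1) is "all subjects who made use of medication at least once during the open-label extension". Section 14.5.4 measures change from the baseline before the double-blind phase and adds: "Summaries of responders at each Visit will be given using the same responder definitions as per the analysis of double-blind phase". Section 9.6.2 seeks IIEF and SEP data after withdrawal only to the end of the double-blind phase.

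**The concern.** The OLAS is defined by any use of gel, but each visit summary rests on the men who have a value at that visit. The group behind the Day 180 mean therefore need not be the group behind the Day 450 mean. With no control, a change between those means has two possible sources: the men changed, or the mix of men changed. The planned summaries do not separate them.

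Men for whom the gel does little have an obvious reason to leave a year of as-required use. If they do so more often than others, the mean among those remaining drifts upward with no change in anyone, and a true decline could be hidden in the same way. In the double-blind phase the protocol meets this problem with continued questionnaires after withdrawal and control-based imputation. It states no counterpart for the extension.

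At stake is what may be said about 12-month efficacy. The double-blind tests are not affected.

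**Working it through.** **Plan's own figure.** The protocol gives no calculated figure for extension efficacy. The SD used below comes from the double-blind sample size in section 14.7, so that calculation was checked first. Inputs: 250 per group; differences 3.2, 11.5 and 12; SDs 5.6, 33 and 33; correlations 0.5, 0.5 and 0.6; two-sided alpha 0.05/3 (critical value 2.394).

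Power per endpoint = Φ(difference / (SD × √(2/250)) − 2.394), with √(2/250) = 0.0894:
- IIEF-EF: 3.2/(5.6 × 0.0894) − 2.394 = 4.00, giving 99.997%
- SEP Question 2: 11.5/(33 × 0.0894) − 2.394 = 1.50, giving 93.3%
- SEP Question 3: 12/(33 × 0.0894) − 2.394 = 1.67, giving 95.3%

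The joint power from the trivariate normal is 90.4%, against 90% stated. It reproduces.

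**Size of the attrition artefact.** Hold each man's IIEF-EF change fixed over time, with SD 5.6 between men. Let a share q leave, and let r be the correlation between poor response and the tendency to leave. The mean among those remaining then rises by

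r × SD × φ(z_q)/(1 − q),

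where z_q is the q-quantile of the standard normal. Both q and r are assumptions, because the protocol gives neither.

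- q = 0.20: φ(−0.842)/0.80 = 0.280/0.80 = 0.350, and × 5.6 = 1.96
- q = 0.30: φ(−0.524)/0.70 = 0.348/0.70 = 0.497, and × 5.6 = 2.78

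| Share leaving | r = 0 | r = 0.25 | r = 0.5 | r = 1 (poorest all leave first) |
|---|---|---|---|---|
| 20% | 0 | 0.49 | 0.98 | 1.96 |
| 30% | 0 | 0.70 | 1.39 | 2.78 |

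Entries are the rise in observed mean IIEF-EF change, in points, with no man changing. As a check, a logistic leaving model with an odds ratio of 2 per SD of poorer response gives 0.72 points at 20% and 1.06 at 30%, inside the r = 0.25–0.5 range.

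**A pull the other way.** In Appendix 1 (18.1), IIEF Questions 1–5 score 0 when there was no sexual activity or no attempt, and Question 15 scores 1–5. A man who stays but is inactive therefore has an IIEF-EF of 1 to 5, within the severe band of section 9.5 (10 or below). Since the extension sets no minimum number of attempts, such men lower the observed mean.

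**Responder percentages.** If p is the percentage among men with a value and a share q of the OLAS has none, counting those men as non-responders gives p × (1 − q). At 20–30% missing, that is 0.8 to 0.7 of the observed-case figure.

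**The case against.** **Purpose.** The extension is mainly a safety study. Section 14 puts safety first, section 14.7 sets the 450 men by regulatory requirement, and no test or claim of maintained effect is planned. Observed-case description is usual in that setting. This stands and limits the weight of the point. Efficacy to 12 months is nevertheless a listed objective, and section 8.2.3 justifies the extension dose partly by what it will show about efficacy.

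**Visibility and the SAP.** Counts of observed values will be shown, raw data listed and withdrawal reasons recorded, and section 14.5.2 leaves further missing-data detail to the SAP. This also stands in part. But counts show that men left, not whether they were poor responders, and the protocol itself fixes the observed-data rule in two places.

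**Certainty.** A reader might infer that the means must improve, or take 2.8 points as the expected bias. The documents support neither. The artefact is zero if leaving is unrelated to response, 2.8 needs 30% to leave strictly in order of poor response, and inactive men who stay pull the other way. Nor is entry selection clearly upward: men from placebo or a lower dose may join because they responded poorly.

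**Responder denominator.** Section 14.5.4 names none. That it means men with a value is an inference from the observed-data rule.

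**SEP and gel use.** A reader might also infer that extension SEP percentages mix attempts with and without gel, because the five SEP items (18.2) do not ask about it. The documents do not establish this. Section 8.2.3 says medication use will be assessed in the open-label analyses, tubes are returned at each visit, and section 14.6.4 times adverse events from the last dose, which suggests that dose timing is recorded. Appendix 1 need not list every data field.

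**Conclusion.** The point holds in a conditional form. Under the stated rule, a maintained or rising mean across extension visits cannot be told apart from response-related attrition. With SD 5.6 and an assumed 20–30% leaving, the artefact is 0 if leaving is unrelated to response, about 0.5–1.4 IIEF-EF points at correlations of 0.25–0.5, and 2.0–2.8 points only in the extreme case. For scale, section 14.7 assumes a drug effect of 3.2 points, but that is a between-arm difference, which the extension does not estimate. Because inactive men who stay lower IIEF-EF, the net direction is uncertain.

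The observed-data tables are not wrong as description. They are insufficient for a statement about persistence. The consequence is moderate: a secondary, descriptive objective is affected, while the primary tests and their power are not. The case for acting is that the remedy is cheap.

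**What to change.** In section 14.5.4 (open-label extension), keep the observed-data tables and add:

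1. IIEF-EF and SEP at Week 12 and at each extension visit for the same men (those with Day 450 data), by previous double-blind arm, with the last values of men who left shown separately. The split is needed because in three of the four arms Week 12 was on placebo or a lower dose than the extension gel. The same-men table removes change in the mix of men but still describes only those who stayed, so the leavers' values belong beside it.
2. The responder percentage at each visit with the whole OLAS as denominator, men with no value counted as non-responders, beside the observed-case percentage. Label it a conservative bound, since men also leave for reasons other than poor response.
3. A sentence saying that observed visit means alone do not show maintained efficacy.

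If gel use per attempt is already captured, also report SEP for attempts with gel. This point does not require a new ePRO item.

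The cost is a few descriptive tables from data already collected, and a 12-month responder rate that is lower in the bound than in the observed-case table.

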14.1 Analysis Sets

The following analysis sets will be used for the statistical analysis of the double-blind phase:

- The **randomised set** will consist of all subjects who were randomised to a treatment
- The **safety set** will consist of all subjects in the randomised set who made use of the medication at least once. In the case of randomisation/treatment errors, subjects will be analysed according to treatment received

- The **full analysis set** (FAS) will consist of all subjects in the randomised set who made use of the medication at least once. In the case of randomisation/treatment errors, subjects will be analysed according to randomised treatment
Primary and secondary analyses will be performed on the FAS.
- The **per protocol set** (PP) will consist of all subjects in the FAS who completed the 12-week treatment period without major protocol violations and who have valid IIEF, SEP Question 2 and SEP Question 3 assessments at Week 12 (Visit 5)

Analysis sets will be identified prior to the unblinding of the study data. The efficacy analysis will be performed as randomised; i.e. a subject will be assigned to the treatment he was initially allocated, irrespective of what treatment was actually applied, and whether or not treatment was discontinued while questionnaire data was collected (see [Section 9.6](#) Withdrawal of Subjects).

In order to assess the consistency of results, sub-group analyses will also be performed according to three subject baseline ED severity groups:

- Mild (IIEF-EF domain score of 17–25)
- Moderate (IIEF-EF domain of 11–16)
- Severe (IIEF-EF domain of ≤ 10)

The following analysis set will be used for the statistical analysis of the open-label extension phase:

- The **open-label analysis set** (OLAS) will consist of all subjects who made use of medication at least once during the open-label extension.

